7.1 Evaluations for ALL Subjects

PART A

Cohort 1: Subject will be monitored at Day 1 and Day 5 of week 1, and then once per week during weeks 2, 3, 4, 5, 6, 7, 8.
PK samples will be drawn on Day 5 of Trial Week 1: pre-morning dose and 0.5, 1, 2, 4 and 8 hours post-morning dose of Day 5.

Cohort 2: TD1, and then once per week during weeks 2, 3, 4, 5, 6, 7, and 8.

PART B[‡]

Subjects of Cohorts 1 and 2 will be monitored at study visits at weeks 10, 12, 16, 20 and 24. CS dosing can be changed during Part B.

PART C[§]

Subjects of Cohorts 1 and 2 will be monitored at study visits every 8 weeks until week 76. Background medications, CS and other background medications can be changed during Part C, while TOFA remains stable.

Follow-up Period

All subjects who discontinue TOFA treatment at any time post-baseline will have a follow up phone call 10 weeks after the last TOFA dose to monitor for the development of safety events.

7.1.1 Disease activity

- SLEDAI-2K and BILAG-2004 ^{17,20}
- Physician Global Assessment of SLE activity (visual analog scale ; 0-10)

[‡] Roll-over subjects in SLE-CL clinical remission may enter Part B as early as week 4

[§] as early as week 8 for subjects with clinical remission of SLE -CL and off CS

- CLASI Activity Score¹⁶

7.1.2 Patient-reported outcomes

- Well Being Assessment (visual analog scale ; 0-10)
- Pain (visual analog scale ; 0-10)
- SKINDEX-29 (appendix 4)¹⁵

7.1.3 Other outcome measures

- SLICC/ACR damage index²¹
- CLASI Damage Index¹⁶

7.1.4 Laboratory parameters

- ESR
- Hematology
- Clinical chemistry
- C3,C4, dsDNA-antibodies
- Urine PC ratio
- Quantitative EBV and CMV PCR

7.2 Evaluations Performed in Select Subjects

7.2.1 Photography & skin biopsy

A subset of up to 3-5 subjects from either Cohort 1 or Cohort 2 will be asked to participate in serial photography of lesions on the back, face or the extremities. Picture will be obtained three times during the study by a trained individual or medical photographer, starting from baseline (also see Schedule of Events).

Subjects agreeing to participate in photography will also be asked to consent to two skin biopsies. At each of the two biopsy sessions 2 skin samples will be obtained (approximately 3 mm in diameter) by means of punch biopsy. The first two skin biopsy samples will be taken from an active SLE-CL lesion located over the back or the extremities during week 1. The second two skin biopsy samples will be taken from the initial lesion, in close geographical proximity to the site of the initial biopsy, between weeks 8 and 15.

Prior to taking the skin biopsy the area will be numbed with topical or injectable lidocaine.

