4.3 Exploratory Objective(s) & Endpoint(s)

Exploratory objectives

Part A:

- To evaluate single cell expression patterns of skin biopsies of affected and non-affected skin with TOFA therapy
- To examine changes in interferon α/γ receptor, STAT phosphorylation patterns with TOFA therapy using immunohistochemistry
- To investigate mRNA expression patterns in peripheral blood upon treatment with TOFA with focus on interferon regulated genes

Parts B and C:

- To evaluate steroid sparing properties of TOFA for SLE-CL
- To evaluate TOFA effect of overall disease activity in SLE as measured by the SLEDAI and BILAG
- To evaluate effects of TOFA on quality of life as measured by the Skindex (appendix 4) and overall well-being

Exploratory endpoints at week 4, 8, 12, 24, 52, and 76

Part A: Pharmacodynamics (PD)

- PD parameters include assessment of inhibitory effect of TOFA on expression of IL-2 responsive target genes downstream of the JAK/STAT pathway, such as FOXP3, SOCS3, IL-2R α , interferon - γ and granzyme B.

Parts B and C:

- Decrease of absolute dose of systemic CS from baseline
- Decrease of body weight adjusted CS dose from baseline
 - CS dosing is measured in prednisone-equivalents
- Proportion of subjects who discontinue systemic CS
- Proportion of subjects with cutaneous relapse
- Change of BILAG score from baseline¹³
- Absolute value and percent change in plasma: Complement C3 and C4d, autoantibodies (anti-dsDNA)
- Change in number of inflamed joints from baseline¹⁴
- Change in SKINDEX score from baseline¹⁵
- Change of CLASI damage score¹⁶ from baseline
- Change in SLEDAI score at each time point
- Change in protein: creatinine ratio at each time point.
- Change in subject's overall well-being at each time point
- Change in subject's ESR
- Proportion of subjects with clinically important reduction in SLE activity at each time point, based on CRV changes compared to baseline
- Proportion of subjects with flare of SLE activity at each time point, as defined by the BILAG¹⁷

Data of subjects who enter Part B before week 8 and/or Part C before week 24 will be considered on a last-observation (LOC) carried forward basis for endpoints of Part A and B, respectively.

5. Study Participants

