7.2.3 Exploratory Pharmacodynamic Biomarkers

A subset of subjects will be asked to participate in translational research studies, performed 2 or 3 times during the study.

- Blood samples for RNA and miRNA level gene expression with focus on interferon regulated pathways
- Interferon γ and interferon α levels
- T cell activation of flow – C1 or POLARIS
- Urine biomarkers
- Single-cell RNA sequencing of skin cells
- Immunohistochemistry of skin cells for phosphorylated STATs and interferons

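### The single-cell objective names affected and non-affected skin, but every planned biopsy sample comes from one active lesion, so no non-affected skin is collected

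*Combined protocol and SAP*

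**What the plan says.** The Part A exploratory objective in Section 4.3 is "To evaluate single cell expression patterns of skin biopsies of affected and non-affected skin with TOFA therapy". Section 8.3 (Effectiveness Analyses) repeats the same two tissue types for exploratory analysis, and so do the exploratory objectives in Appendix 3 part B.

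Section 7.2.1 describes the procedure. Subjects who agree to photography "will also be asked to consent to two skin biopsies", and "At each of the two biopsy sessions 2 skin samples will be obtained". On site it says:

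- Week 1: "The first two skin biopsy samples will be taken from an active SLE-CL lesion", on the back or the extremities.
- Weeks 8 to 15: "The second two skin biopsy samples will be taken from the initial lesion", near the place of the first biopsy.

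Section 7.2.3 lists two laboratory uses of skin: "Single-cell RNA sequencing of skin cells" and "Immunohistochemistry of skin cells for phosphorylated STATs and interferons". Neither entry gives a biopsy site. Footnote 7 to the Section 10 schedule gives biopsy timing but no site. The schedule also marks the skin work as done at one of the two centres only.

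**The concern.** The objective and the procedure do not match. The objective needs two tissue types; the procedure assigns every punch to one of them. This is more than missing detail that a laboratory manual could supply, because Section 7.2.1 leaves no sample unallocated as to site. An investigator who follows it cannot provide non-affected skin, and one who takes normal skin departs from the written procedure.

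At stake is the comparison or reference that non-affected skin would give in the single-cell work. Tissue not taken in week 1 cannot be recovered later. The procedure is also invasive and done in volunteers, so its sites should match its stated purpose.

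**Working it through.** The plan gives no figure to reproduce. The check sets the texts side by side and counts samples.

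**Step 1: tissue required.** Sections 4.3 and 8.3 and Appendix 3 part B all name affected and non-affected skin for single-cell expression. Three consistent statements make a single typing slip unlikely.

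**Step 2: tissue collected under Section 7.2.1.**

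| Session | Samples | Site | Lesional | Non-affected |
|---|---|---|---|---|
| Week 1 | 2 | Active lesion | 2 | 0 |
| Weeks 8 to 15 | 2 | Same initial lesion | 2 | 0 |
| Per subject | 2 × 2 = 4 | | 4 | 0 |

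The section allows up to 3-5 subjects:

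- 3 subjects: 3 × 4 = 12 samples, 0 non-affected.
- 5 subjects: 5 × 4 = 20 samples, 0 non-affected.

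The subject number is a ceiling, so totals may be lower. The zero does not depend on it.

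**Step 3: could another reading supply the tissue?**

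- *Nearness to the first site.* Section 7.2.1 asks that the second pair be taken close to the first biopsy. The same sentence says the samples come from the initial lesion, so this places the punch within the lesion and does not describe skin beside it.
- *A lesion that clears by weeks 8 to 15.* The later samples would then be treated, formerly affected skin. That informs a before/after comparison, but there is still no non-affected sample from week 1, and clearance is not assured.
- *The schedule.* Its rows and footnote 7 give timing only. Columns in the extracted table are displaced, so nothing here rests on their position.

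None of the three yields non-affected skin.

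**Step 4: sample counts under the possible corrections, four punches per subject throughout.**

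| Option | Lesional per subject | Non-affected per subject | Non-affected over 3 to 5 subjects |
|---|---|---|---|
| As written | 4 | 0 | 0 |
| One non-affected sample, week 1 only | 4 − 1 = 3 | 1 | 3 to 5 |
| One non-affected sample, both sessions | 4 − 2 = 2 | 2 | 6 to 10 |
| Narrow the wording, keep the sites | 4 | 0 (none claimed) | 0 |

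**The case against.** The best case for leaving the text alone is that little depends on it. The work is exploratory, in a handful of volunteers at one centre, and Section 8.3 commits to no test, contrast or success criterion for skin expression. The before/after comparison within the lesion survives. So does the separate objective on interferon receptors and "STAT phosphorylation patterns with TOFA therapy using immunohistochemistry", which does not mention non-affected skin. All of this stands, and it limits the weight of the point. It does not remove the mismatch, which can be corrected by wording alone.

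Two stronger readings are tempting, and the documents do not support either.

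- A reader might infer from footnote 7 that only two punches are taken in all, half of what Section 7.2.1 plans. Read literally, the footnote gives one punch per session. But Section 7.2.1 itself uses two biopsies to mean two sessions of two samples, so the footnote may be shorthand. It names no site and has no bearing on the missing tissue.
- A reader might infer that there is too little tissue for two assays, or that one 3 mm punch cannot serve both. The documents do not say how samples are divided between sequencing and immunohistochemistry, nor that both are run on every sample. A per-assay figure would rest on an assumed split.

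Nor do the documents show whether the objective or the procedure is the slip. The point is the inconsistency, not a claim that the sponsor chose to omit normal skin.

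**Conclusion.** The point holds. Section 7.2.1 as written gives 4 lesional and 0 non-affected samples per subject, so the non-affected part of the single-cell objective cannot be met. This rests on the protocol text alone: Section 7.2.1 is the only place that gives biopsy sites, and it accounts for all four samples.

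A reader might go further and conclude that the skin substudy fails or that the trial's main results are weakened. Neither follows. Within-lesion change from week 1 to weeks 8 to 15 and the immunohistochemistry objective remain achievable, and no primary, secondary or safety analysis uses this tissue. It is a minor correction worth making, most usefully before biopsies begin.

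**What to change.** Choose one of two routes. Neither adds a punch.

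**(a) Collect the tissue.** Amend Section 7.2.1 so that one of the two samples, at the week 1 session at least, comes from clinically non-affected skin of the back or extremities, and the other from the lesion. The cost is one lesional punch fewer at each session so changed (4 down to 3 per subject for week 1 only, 4 down to 2 for both sessions), plus IRB review of the new biopsy site. A week 1 sample alone gives a non-affected reference; showing how non-affected skin changes on treatment would need the sample at both sessions.

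**(b) Narrow the claim.** If both lesional punches are needed, keep the sites and delete *and non-affected* from Sections 4.3 and 8.3 and Appendix 3 part B. The trial then claims only within-lesion change from week 1 to weeks 8 to 15. This adds no procedure. The cost is a protocol wording amendment and giving up the non-affected part of the objective.

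Under either route, as a side edit, reword footnote 7 to state two 3 mm samples at each of two sessions, the first in week 1 and the second between weeks 8 and 15.

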6.2 Dosing

TOFA dosing: Twice daily orally

As documented in the TOFA Investigator brochure (Section 6.1; Version March 2016) doses up to 30 mg twice daily were safe and tolerated. However, for the purpose of this study only the dose of TOFA approved for rheumatoid arthritis (5 mg PO BID) will be tested.

Based on TOFA PK in the Rheumatoid Arthritis (RA) population [body weight (BW) ranging from 40 kg - 140 kg)], clearance (CL) of TOFA is not dependent on body weight in adult subjects. Thus, the starting dose of TOFA will be 5 mg orally twice daily, an approved dose of TOFA in adult RA subjects in most countries. Dose escalation will not occur even with lack of SLE-CL improvement.

Corticosteroids (CS):

At study entry, CS dosage must be \leq 20mg/day. CS should be kept stable up to and including week 4.

CS can be decreased starting week 5:

- CS may be decreased for improvement of the CLASI activity score by \geq 50% from baseline and must be tapered for CLASI activity scores of 0 for $>$ 8 weeks (or 2 subsequent study visits, whatever is shorter), provided CS are mainly prescribed for SLE-CL. This will minimize morbidity associated with CS use as much as possible.
- If CS are mainly prescribed for other SLE manifestations besides SLE-CL, then CS can be decreased as per the investigator's decision, even in the setting of complete response of SLE-CL, based on continued improvement of clinical findings of SLE.

Oral CS may be increased above the baseline level up to max of 60 mg/day for new BILAG A or B flares in organ systems other than mucocutaneous organ system (i.e. neurologic, ophthalmologic, musculoskeletal, cardiopulmonary, gastrointestinal, renal, hematological organ systems) but must be returned to baseline dose or lower within 14 days. If this is not achieved then the subject is considered a treatment failure.

- Up to 3 doses of pulse methylprednisolone may be given for new BILAG A or B flares instead.
- CS increases can occur no more than 3 times during the duration of the study, Part A- C.
- Subjects requiring more than 3 CS increases will be withdrawn from treatment phase of study.

Other anti-inflammatory medications used as part of standard of care (SOC) for SLE

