8.1 Pharmacokinetic Analysis

The PK concentration population is defined as all subjects enrolled and treated for whom at least 1 TOFA level or parameters of interest can be determined.

PK parameters of TOFA following multiple-dose oral administration will be derived from the concentration-time profiles using noncompartmental analysis. The observed predose concentration will also be used as the 12-hour concentration in these calculations, assuming steady state. Actual PK sampling times will be used in the derivation of PK parameters.

The plasma PK parameters from noncompartmental analysis (CL/F, Vz/F, AUCt, Cmax, Tmax, and $t_{1/2}$ (if data permit)) on Day 5 will be summarized descriptively by Visit/Day. Plasma concentrations will also be summarized descriptively by PK sampling time. Individual subject concentration-time data will be plotted using actual PK sampling times. Summary profiles (mean and median plots) of the concentration-time data will also be presented. Summary profiles will be presented on both linear-linear and log-linear scales.

The PK parameters such as CL/F and Vz/F may be compared with historical adult RA and JIA patients data using mixed effect modeling approach.

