Medical history, medication		X																					
Tuberculosis assessment		X																					
Serum virology (HBsAg, HCV, HIV, VZV)		X																					
Serum pregnancy test*2		X																					
Urine pregnancy test*2			X		X						X		X		X	X	X	X	X	X	X	X	
Vital sign, weight, height*3		X	X	X	X	X	X	X	X	X	X	X	X	X	X	X	X	X	X	X	X	X	
Investigational Product Dispensing (or as needed)			X				X				X		X	X	X	X	X	X	X	X	X	X	X
Patient Dosing Diary review				X	X	X	X	X	X	X	X	X	X	X	X	X	X	X	X	X	X	X	
Complete physical examination		X	X			X					X		X	X	X	X	X	X	X	X	X	X	X
Laboratory Assessment																							
Hematology		X	X	X	X	X	X	X	X	X	X	X	X	X	X	X	X	X	X	X	X	X	
Clinical chemistry		X	X	X	X	X	X	X	X	X	X	X	X	X	X	X	X	X	X	X	X	X	
Urinalysis incl. sediment		X	X			X					X		X	X	X	X	X	X	X	X	X	X	
Urine protein: creatinine ratio		X	X			X					X		X	X	X	X	X	X	X	X	X	X	
Complement C3, C4,			X			X					X		X	X	X	X	X	X	X	X	X	X	
ANA*4 and anti-ds DNA Abs			X			X					X		X	X	X	X	X	X	X	X	X	X	
ESR			X			X					X												X
Efficacy																							
CLASI		X	X	X	X	X	X	X	X	X	X	X	X	X	X	X	X	X	X	X	X	X	
Photography (selected)			X							X													
SLICC/ACR damage index			X								X												X
SLEDAI-2K, MD Global Assessments, BILAG			X			X					X		X	X	X	X	X	X	X	X	X	X	
Patient's Global Assessment, Skindex			X			X					X		X	X	X	X	X	X	X	X	X	X	
Pharmacokinetic																							
Plasma TOFA-Part A (Cohort 1) *5			X*6																				
Pharmacodynamic																							
**Gene expression profiling of IL2 mediated genes in whole blood					X						X						X						
**Phosphospecific flow cytometry of blood T-cells & other relevant cells					X						X						X						
**SC-RNA SEQ in skin biopsies (selected)				X														X					
**Skin biopsy (selected) *7			X														X *7						
Safety																							
Adverse events/SAE		X	X	X	X	X	X	X	X	X	X	X	X	X	X	X	X	X	X	X	X	X	
Concomitant medications		X	X	X	X	X	X	X	X	X	X	X	X	X	X	X	X	X	X	X	X	X	
TT, diphtheria, varicella, influenza titer; EBV and CMV PCR		X															X						

¹*Part A - Day 5 after TD1

²Females only

³Height only at screening

⁴ANA only at baseline on TD1

⁵ A total of 24.5 mL of blood will be taken at these visits for pharmacodynamics tests

⁶PK samples will be drawn on Day 5 of Trial Week 1. re - morning dose for Day 5 and at 0.5, 1, 2, 4 and 8 hours post morning dose.

⁷ Two 3mm punch biopsies will be collected. 1st punch collected during week one. 2nd punch collected between weeks 8-15.

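### The first skin biopsy may be taken at any time in week 1 with no requirement that it precede the first TOFA dose, so the only skin comparison may lack a pre-treatment sample

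*Combined protocol and SAP*

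**What the plan says.** Section 7.2.1 (Photography & skin biopsy) describes two biopsy sessions in a subset of up to 3-5 subjects from either cohort. It sets the first session at an active lesion "located over the back or the extremities during week 1", with no mention of the first dose. Session two, at the same lesion, falls "between weeks 8 and 15". Footnote 7 of the Schedule of Assessments (Section 10) gives the same timing for the first sample: "1st punch collected during week one".

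Section 6.2 gives the dosing frequency: "TOFA dosing: Twice daily orally". Section 7.1 says of Cohort 1: "Subject will be monitored at Day 1 and Day 5 of week 1". Cohort 2 has TD1 and then weekly visits from week 2, so TD1 is its only named visit in week 1.

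The tissue serves the exploratory Part A objectives in Section 4.3: single-cell expression in skin, and changes in interferon receptor and "STAT phosphorylation patterns with TOFA therapy using immunohistochemistry".

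**The concern.** These objectives ask what changes in skin once TOFA is given, and the two biopsy sessions are the only skin samples in the plan. The first therefore acts as the reference, whatever it is called. If it is taken after dosing has begun, both members of the pair are on treatment, unless the subject has stopped TOFA before the second session.

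The marker makes this matter. The introduction explains that Jak phosphorylates STAT and that TOFA inhibits Jak, so phosphorylated STAT lies directly downstream of the drug's target. An on-drug first sample may already reflect part of the effect. The degree could differ between subjects, because the window lets them be biopsied on different days. A pre-treatment sample cannot be obtained once dosing has started.

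**Working it through.** The plan gives no figure for this point, so there is none to reproduce. The check has four steps.

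**1. Is a pre-dose sample required anywhere?** Section 7.2.1 and footnote 7 name only the week. No screening biopsy is scheduled. The protocol does state pre-dose timing where it wants it: the TD1 urine pregnancy test (Section 5.1, criterion 7) and the first Day 5 PK sample (Sections 3 and 7.1). The biopsy carries no such condition.

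**2. Does the schedule fix the day?** The first biopsy mark appears under Visit 1. The Cohort 1 plasma TOFA mark appears in the same column, and footnote 6 puts those samples on Day 5. The Visit 1 heading also carries a footnote pointing to Day 5. The mark for single-cell sequencing of the same tissue appears one column later. The column alignment in the available text is uncertain, so I rest nothing on it alone. At best the mark means TD1, and it still does not say before dosing.

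**3. How many doses could precede the first biopsy?** Inputs: 2 doses per day (Section 6.2), starting on TD1. With a morning first dose, doses before the morning dose of day d = 2 × (d − 1).

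| Time of first biopsy | Prior doses |
|---|---|
| TD1 before dosing | 0 |
| TD1 after dosing | 1 to 2 |
| Day 5 before the morning dose | 2 × 4 = 8 |
| Day 5 after the morning dose | 8 + 1 = 9 |
| End of Day 7 (limit of the window) | 2 × 7 = 14 |

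With an evening first dose, each count after TD1 is one lower, so Day 5 gives 7 to 8.

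**4. What does that imply for exposure and for the comparison?** Section 8.1 analyses Day 5 plasma data "assuming steady state". As a cross-check, the fraction of steady state after n doses is 1 − 2^(−12n / t½). Appendix 1 gives half-lives of 1.77 to 2.62 h in juvenile arthritis, used here as a proxy; 4 to 6 h is my assumed wider range.

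| Half-life | After 1 dose | After 2 doses |
|---|---|---|
| 1.77 h | 99.1% | 99.99% |
| 2.62 h | 95.8% | 99.8% |
| 4 h (assumed) | 87.5% | 98.4% |
| 6 h (assumed) | 75.0% | 93.8% |

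Plasma exposure by Day 5 is thus at steady state on any of these values. This describes plasma, not skin. If the first sample already shows a fraction f of the effect present at the second, the observed change is (1 − f) × the true change: all of it at f = 0, none at f = 1. No document gives f or a time course for phosphorylated STAT in lesional skin. The likely direction is toward no change; the amount is unknown.

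With 3 to 5 subjects, one on-treatment first sample would touch 1/5 to 1/3 of the pairs (20-33%). That illustrates how few pairs there are and does not estimate how often it would happen.

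**The case against.** The best defence is that TD1 was probably intended. The biopsy mark sits with other TD1 procedures, the same subjects are photographed from baseline, and TD1 is the only named week 1 visit for Cohort 2. On that reading the plan lacks only the word pre-dose. This stands as a reason to think a pre-treatment sample is likely in many cases. It does not make one assured: Cohort 1 has a Day 5 visit in the same window, and a TD1 biopsy after dosing also complies.

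Second, a reader might infer from the width of the window that first biopsies would follow as many as 14 doses. That is the arithmetic limit, reached only after the Day 7 evening dose and outside any named visit. At the named visits the count is 0 to 2 (TD1) or, for a morning start, 8 to 9 (Day 5, Cohort 1 only).

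Third, a reader might take plasma steady state as showing that skin inhibition is already complete. The documents do not support that. With a half-life of 2.62 h, about 2^(−12/2.62) = 4% of the drug remains 12 h after a dose, so time since the last dose may matter as much as the number of doses, at both biopsies.

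Fourth, the objective is exploratory, in a handful of volunteers, and Section 8.3 attaches no test to it. That limits the consequence and is accepted.

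**Conclusion.** The point holds in a limited form. As written, the window permits a first biopsy on treatment, and neither the text nor the schedule rules it out. At Day 5 in Cohort 1 that means 8 to 9 prior doses, assuming a morning start on TD1 and full adherence. The skin comparison would then probably be biased toward no change. That direction rests on the drug's stated mechanism; the size cannot be computed from the documents.

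It would go too far to say that the plan has a mislabelled baseline biopsy or that the pre-treatment reference is lost. In Section 7.2.1 the word baseline belongs to the photographs; the first biopsy is a reference only by function. A pre-dose TD1 biopsy is fully allowed, so the reference is not assured rather than absent.

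The effect is confined to the exploratory skin objectives (STAT phosphorylation, interferon receptor and single-cell expression) in up to 3-5 subjects. The primary PK and safety endpoints and the CLASI endpoint are unchanged. It is worth correcting because the correction is cheap and the sampling is invasive.

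**What to change.** In Section 7.2.1 and footnote 7, replace the week 1 window with: *on TD1, after eligibility is confirmed and before the first dose*. Align the schedule marks for the biopsy and for single-cell sequencing with that day.

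Record the number of doses taken and the time since the last dose at both biopsies. Report any first biopsy taken after dosing separately from the pre/post-treatment change summary. This keeps the sample without mixing the two kinds of pair.

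A screening biopsy would be a poorer choice. Section 5.1, criterion 4 requires the CLASI threshold at both screening and baseline, and the schedule rechecks eligibility on TD1, so a subject could be biopsied and never dosed.

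The cost is small: no added biopsies and no added visits, but a tighter scheduling window on TD1.
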